7.2.3 Reporting of Non-serious Events of Special Interest

Non-serious AEs of special interest must be reported by the investigator to the Sponsor immediately (i.e., no more than 24 hours after learning of the event; as per SAE reporting procedure in Section [7.2.2](#)). AEs of special interest for this study include the following:

- Cases of an elevated ALT or AST in combination with either an elevated bilirubin or clinical jaundice (Section [7.1.3](#))
- Suspected transmission of an infectious agent by the study drug

7.2.4 Pregnancy

A female subject must be instructed to stop taking the study medication and immediately inform the investigator if she becomes pregnant during the study. The investigator should report all pregnancies within 24 hours to the Sponsor, using the Pregnancy Report eCRF. The investigator should counsel the subject, and discuss the risks of continuing with the pregnancy and the possible effects on the fetus. Monitoring of the subject should continue until conclusion of the pregnancy. Pregnancies occurring up to 90 days after the completion of the study medication must also be reported to the investigator. Subjects that become pregnant during the treatment period will be withdrawn from the treatment period and continue into the follow-up period.

Pregnancy occurring in the partner of a male subject participating in the study should be reported to the investigator and the Sponsor. The partner should be counseled, the risks

of continuing the pregnancy discussed, as well as the possible effects on the fetus. Monitoring of the subject should continue until conclusion of the pregnancy.

NOTE: The investigator should fill out a Pregnancy Report eCRF only if the pregnant partner has signed a Pregnant Partner Data Release Form.

In the event that the EDC system is unavailable, a Pregnancy Report worksheet and Pregnancy Fax Coversheet should be completed and faxed to Roche Safety or its designee within 1 working day after learning of the pregnancy.

7.3 WARNINGS AND PRECAUTIONS

Alpha interferons, including PEG-IFN, may cause or aggravate fatal or life-threatening neuropsychiatric, autoimmune, ischemic, and infectious disorders. Subjects should be monitored closely with periodic clinical and laboratory evaluations. Therapy should be withdrawn from subjects with persistently severe or worsening signs or symptoms of these conditions. In many, but not all cases, these disorders resolve after stopping PEG-IFN therapy.

To date, no teratology or reproduction studies have been conducted in humans with PEG-IFN. Primate teratology studies indicate an increased incidence of spontaneously aborted fetuses in pregnant rhesus monkeys (*Macaca mulatta*) receiving high doses of intramuscular Roferon[®]-A [51]. Studies with Roferon[®]-A in non-pregnant rhesus monkeys have shown menstrual cycle irregularities, including prolonged menstrual periods. Male fertility and teratological evaluations have yielded no significant adverse effects to date. However, sexually active males will be excluded or discontinued from this study if not utilizing reliable contraception during the treatment/principal observation period and during the initial 24-week follow-up period.

Interferons are human proteins that show a substantial degree of species specificity, making extrapolation of animal study data to humans of questionable value. Investigations have been conducted in normally cycling healthy females using non-recombinant human leukocyte interferon. Results demonstrate a significant reduction of serum estradiol and progesterone concentrations during the treatment interval [52].

There are no adequate, controlled studies of any IFN in pregnant females. Therefore, extreme care must be taken to avoid pregnancy during the study in female subjects, and female partners of male subjects taking PEG-IFN. Sexually active females will be excluded/discontinued from this study if not utilizing effective contraception at enrollment and will be discontinued from study treatment if not using effective contraception during the initial 24-week follow-up period. Females who are pregnant or breast-feeding will also be excluded. A pregnancy test will be performed for each female of childbearing potential prior to baseline and switch baseline, and at any time secondary amenorrhea of more than 1 week occurs. In addition, subjects treated with PEG-IFN will have a pregnancy test performed according to the schedules in [Table 2](#) and [Table 4](#). If

pregnancy occurs in a subject or partner of a subject during the PEG-IFN treatment period or up to 3 months after PEG-IFN treatment, the cases should be handled as described in Section 7.2.4.

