3.1 OVERVIEW OF STUDY DESIGN AND DOSING REGIMEN

This is a 2:1 randomized, controlled, parallel-group, open-label, multicenter study of PEG-IFN treatment compared to an untreated control ([Figure 1](#)). Subjects without advanced fibrosis/cirrhosis will be randomized 2:1 to PEG-IFN treatment (Group A) or untreated control (Group B), respectively. Subjects with advanced fibrosis will be assigned to PEG-IFN treatment (Group C). Subjects in Groups A and C will receive PEG-IFN for 48 weeks. The first 48 weeks from randomization will be referred to as the treatment period for Groups A and C and the principal observation period for Group B. The primary endpoint will be assessed 24 weeks after the end of treatment/principal observation period.

Forty-eight weeks after randomization, PEG-IFN will be offered to subjects in the Group B untreated control group who have not experienced HBsAg seroconversion. This offer will be available for up to 1 year following Week 48. If eligible, these subjects will enter the switch arm, where they will receive PEG-IFN for 48 weeks.

The screening period will be up to 35 days. For Group A, Group B non-switch, and Group C subjects the study length is approximately 6 years (1-year treatment/principal observation period and 5 years of follow-up). For Group B switch subjects the study length is up to approximately 8 years (1-year principal observation period, up to 1 year follow-up whilst deciding whether to switch, 1-year switch treatment period, and 5-year follow-up period).

Figure 1 Schematic of Study Design

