- ^j Within 2 years prior to baseline **or** within 9 months prior to baseline for subjects with advanced fibrosis.
- ^k Subjects in site-specific liver elasticity sub-study only.
- ^l Parameter does not need to be repeated at re-screening if performed within 6 months prior to baseline, unless dictated by a change in the subject's medical condition or the parameter accounted for the original screen failure.

Table 3 Schedule of Assessments and Procedures—Group B (Untreated Control)

Assessment/Procedure	Screen (days)	BL (days)	Principal Observation Period (weeks)				Initial Follow-up (weeks Post-End of Principal Observation Period)		Long-Term Follow-Up (years Post-End of Principal Observation Period)					
	-35 to -1	1	12	24	36	48 ^a	12 ^a	24 ^a	1 ^a	1.5 ^b	2	3	4	5
Informed Consent/Assent ^c	x													
Complete medical history, including family history of HBV	x													
Physical examination	x							x						
Symptom-directed physical examination		x	x	x	x	x	x							
Vital signs	x	x	x	x	x	x	x	x						
Weight ^d	x	x ^f	x	x	x	x	x	x	x		x	x	x	x
Height ^{d,e}	x	x ^f	x	x	x	x	x	x	x		x	x	x	x
Parental height ^g		x												
Ultrasound ^{h,i}	x													
Ophthalmology exam ^{i,j}	x													

^a Eligible subjects may switch at any time between Week 48 and 1 year following Week 48 at which time subjects will continue on the Switch Schedule of Assessments and Procedures.

^b By telephone.

^c Informed Consent obtained from legal guardian, and assent obtained from child if appropriate.

^d Measurements must be taken using the same instruments in the same individual.

^e Using stadiometer and taking the mean of three readings.

^f Weight and height to be provided to IXRS.

^g From consenting biological parents.

^h To rule out hepatocellular carcinoma. Further liver imaging assessment may be performed if necessary.

ⁱ Within 6 months prior to baseline; repeat only if any change in medical condition.

^j By ophthalmologist (*pediatric ophthalmologist is recommended*) and including fundoscopic examination *with dilation*, visual acuity assessment, visual field testing (*confrontation test is recommended for younger children*), and color visual testing. Any subject who develops ocular symptoms should receive a prompt eye examination by an ophthalmologist and additional examinations as necessary.

Table 3 Schedule of Assessments and Procedures—Group B (Untreated Control) (cont.)

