6.5.2 Assessment of Compliance

At each visit, compliance with the study requirements will be reinforced.

Subject compliance with taking study drug as required will be assessed by maintaining adequate study drug dispensing records and review of the SMD. The investigator is responsible for ensuring that dosing is administered in compliance with the protocol. Delegation of this task must be clearly documented and approved by the investigator.

It is mandatory that each injection (date and volume) be recorded in the drug diary and initialed by the person giving the injection (see Section 5.5). Subjects will be asked to return used drug containers at each visit, along with the drug diary. Returned drug containers will be counted and justified against the diary entries by study site personnel. Each verified injection will be recorded on the eCRF at each visit. Unused study drug should be returned at the end of the treatment period (i.e., Week 48). Under no circumstances should the treatment period for any subject extend beyond the allocated 48 weeks.

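### Protocol 7.3 stops girls' study treatment for a contraception lapse only after PEG-IFN has ended, and removes boys from the whole study even when untreated or off drug

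*Protocol*

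**What the plan says.** Protocol 7.3 (Warnings and Precautions) treats the sexes differently.

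- **Girls.** There are two rules. At entry: "Sexually active females will be excluded/discontinued from this study if not utilizing effective contraception at enrollment". Later, a girl "will be discontinued from study treatment if not using effective contraception during the initial 24-week follow-up period".
- **Boys.** There is one rule: "sexually active males will be excluded or discontinued from this study if not utilizing reliable contraception during the treatment/principal observation period", with the initial 24-week follow-up added in the same sentence.

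The same section gives its reason as avoiding pregnancy in female subjects and in "female partners of male subjects taking PEG-IFN". It also wants a pregnancy handled if it occurs in a subject or the "partner of a subject during the PEG-IFN treatment period or up to 3 months after PEG-IFN treatment".

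On the length of treatment, Protocol 6.5.2 says: "Under no circumstances should the treatment period for any subject extend beyond the allocated 48 weeks".

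**The concern.** A rule that stops a drug has to apply while the drug is being given. For girls, the only order to stop study treatment is attached to a period when dosing is over, and the weeks on drug are not named. A site that learns in, say, Week 20 that a girl is no longer using contraception has no instruction on whether to stop PEG-IFN.

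For boys there is an instruction, but it ends participation in the study rather than exposure to the drug. It applies equally to Group B boys who receive nothing and to boys who have finished treatment, and for them removal reduces no exposure. What is lost is follow-up. For a boy removed early that includes the primary endpoint. For a treated boy it includes the visits at which a partner's pregnancy in the 3 months after PEG-IFN might come to light.

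**Working it through.** No formula applies to the main point. The check is a comparison of periods and of what other sections provide.

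**1. Does the girls' order overlap with dosing?**

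- Groups A and C: PEG-IFN runs from Week 0 to Week 48 at most (3.1, 6.5.2). The initial follow-up is the 24 weeks after the end of treatment (5.3), that is Week 48 to 48 + 24 = Week 72 for a girl who completes treatment. Overlap with dosing: 0 weeks. If she stops early, follow-up starts after she has stopped (4.6.1), so the overlap is again 0.
- Group B without switch: no PEG-IFN in either period. Overlap: 0 weeks.
- Group B with switch: a girl may start PEG-IFN from Week 48, which falls in the calendar time of Group B's initial follow-up. Table 3, footnote a, deals with this: "at which time subjects will continue on the Switch Schedule of Assessments and Procedures". Her initial switch follow-up comes after switch treatment (5.3). Overlap: 0 weeks.

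**2. Does another section say what to do about a lapse on drug?**

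| Section | What it provides | Acts on a lapse on drug? |
|---|---|---|
| 4.3, 4.8.2 | Willingness to use contraception, judged at entry or at switch | No |
| 4.6.2 | Investigator may withdraw a child from the study for non-compliance | Discretionary; removes from the study |
| 5.3.2, Tables 2 and 4 | Scheduled pregnancy tests, plus a test for secondary amenorrhea of more than 1 week | Detects a pregnancy, does not prevent one |
| 6.2.1 | Lists pregnancy among reasons to consider stopping | No |
| 6.5.2 | Compliance reinforced at each visit | General; no action named |
| 7.2.4 | Stop drug once pregnant, continue into follow-up | No, only after pregnancy |

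The cover is partial. None of these tells a site whether to stop PEG-IFN before a pregnancy occurs.

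**3. Whom does the boys' order reach?**

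Section 3.1 defines the principal observation period as Group B's first 48 weeks, which are untreated. The initial follow-up is off drug. Besides boys on PEG-IFN, the order therefore reaches untreated boys and boys who have finished treatment.

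**4. What happens to the data of a removed boy?**

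- Removed before Week 48: 4.6.2 asks for the Week 48 assessments at withdrawal, so there is no follow-up Week 24 reading. He stays in the ITT population if dosed (Group A) or randomized (Group B) under SAP 4.1.1. Protocol 8.2.1.1 and SAP 4.4.1.3 then score him as a non-responder. The LOCF sensitivity analysis in SAP 4.4.1.3 would use his last value instead.
- Removed after Week 48 but before follow-up Week 24: 4.6.2 asks for the follow-up Week 24 assessments at withdrawal, and these include HBeAg and anti-HBe. Whether an early reading counts for the endpoint depends on time windows that SAP 4.2 leaves to another document.

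**The case against.** The strongest reply for girls is that the slip is one of drafting. Section 4.3 names the treatment/principal observation period and the initial follow-up for both sexes, so the intended meaning can be guessed, and a careful investigator would counsel and stop the drug anyway. That is plausible. But it remains an inference, and the sentence as written is an operative safety rule that cannot be carried out.

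For boys, the reply is that both arms accept the same contraception condition at entry and that Group B children may start PEG-IFN from Week 48, so equal treatment of the arms is consistent. It is consistent, but 4.8.2 tests willingness again before any switch drug is given. Removing an untreated boy beforehand adds no protection from the drug.

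Several stronger readings are tempting and are not supported:

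- A reader might infer that the boys' rule contradicts 6.2.1 and 7.2.4. Those sections concern other triggers (toxicity and pregnancy). They show a different approach, which is to stop the drug and keep the child in follow-up, but 7.3 does not contradict them. Section 4.6.2 discourages unnecessary withdrawal but also allows it for non-compliance.
- A reader might infer from the spacing of the scheduled tests that a pregnancy would go unnoticed for weeks of dosing. The amenorrhea-triggered test is a second route to detection.
- A reader might infer that every removed boy loses his endpoint. Section 4.6.2 asks those leaving between Week 48 and follow-up Week 24 to complete the Week 24 assessments.
- A reader might infer that all contact with a removed boy is lost. Section 4.6.2 has children who leave follow-up asked whether they may still be contacted.
- A reader might infer that the switch period is uncovered. Table 4 itself heads those weeks as a treatment period, so the existing wording may include them. It is still better to name them.

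**Conclusion.** The point holds as a minor correction of safety wording and retention. The girls' order cannot operate in any group (overlap with dosing 0 weeks), and a lapse on drug is left to site discretion. The boys' order goes further than ending drug exposure, and a boy removed before Week 48 loses his follow-up Week 24 endpoint and is scored as a non-responder.

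The number affected is not given. It would be children under 18 at baseline who are sexually active, declared willingness at entry and later lapsed, so it is probably small. Protocol 8.2.2 also makes some allowance for withdrawals. No claim about power or bias follows. A reader might infer a fixed shift in the treatment difference per removed boy from the design rates of 32% and 10%. For a treated boy this is not supported: the design rate assumes a full course, and the remedy would stop his drug too, so his chance of response is unknown.

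The conclusion for boys assumes that non-use in either named period is enough. The sentence joins the periods with *and*. If non-use in both were required, removal could come only in follow-up and the endpoint loss would be smaller.

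**What to change.** In Protocol 7.3, keep the exclusion at enrollment of sexually active girls not using effective contraception, and of boys not willing to use it (as in 4.3). Replace the rest of the two sentences with:

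> Sexually active females and males who are not using effective contraception while receiving PEG-IFN (treatment or switch treatment period) will be counselled. If this is not corrected, they will be discontinued from PEG-IFN and kept in follow-up, including the follow-up Week 24 visit. Subjects not receiving PEG-IFN (Group B, or after the end of treatment) will be counselled and will not be withdrawn from the study for this reason alone.

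Sections 4.3, 4.8.2 and 7.2.4 and the pregnancy-test schedule stay as they are. The cost is two sentences in one section and a few more follow-up visits for children who would otherwise have been removed. The contraception requirement for Group B remains a condition of entry, and is checked again at switch, but a breach while untreated no longer ends participation.

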8. STATISTICAL CONSIDERATIONS AND ANALYTICAL PLAN

8.1 PRIMARY AND SECONDARY STUDY ENDPOINTS

8.1.1 Primary Endpoints

- HBeAg seroconversion (loss of HBeAg and presence of anti-HBe) at the 24-week post-*end of treatment/principal observation period* follow-up visit

8.1.2 Secondary Endpoints

- Loss of HBeAg, HBsAg seroconversion (loss of HBsAg and presence of anti-HBs), loss of HBsAg, quantitative serum ALT, proportion of normal ALT, quantitative HBV-DNA, suppression of HBV-DNA < 100,000 copies/mL (<20,000 IU/mL), < 10,000 copies/mL (<2,000 IU/mL), undetectable and change from baseline, combined endpoint of HBeAg seroconversion and HBV-DNA < 100,000 copies/mL (<20,000 IU/mL), and combined endpoint of HBeAg seroconversion and HBV-DNA <10,000 copies/mL (<2,000 IU/mL) at the end of treatment/principal observation period, 24 weeks after end of treatment/principal observation period, and 1, 2, 3, 4 and 5 years after end of treatment/principal observation period.
- Persistence of HBeAg seroconversion (loss of HBeAg and presence of anti-HBe) at the end of treatment/principal observation period, and 1, 2, 3, 4, and 5 years after end of treatment/principal observation period.
- Descriptive change from baseline in liver elasticity (for subjects enrolled in the liver elasticity sub-study) at the end of treatment/principal observation period, and 24 weeks and 2 years after end of treatment/principal observation period.

8.1.3 Safety

Safety of the treatment will be evaluated by AEs (including SAEs and non-serious AEs of special interest), laboratory tests, vital signs (blood pressure, heart rate, temperature), and growth (weight and height).

8.1.4 Pharmacokinetic

PK parameters (e.g., CL/F, V/F, AUC, C_{max}, etc.) of PEG-IFN will be evaluated in subjects following administration of a new BSA-based dosing regimen over the first 24 weeks of treatment.

8.2 STATISTICAL AND ANALYTICAL METHODS

8.2.1 Statistical Model

8.2.1.1 Primary Variables

The primary efficacy parameter is HBeAg seroconversion (defined as absence of HBeAg and presence of HBeAb) determined 24 weeks after the end of treatment/principal

observation period. Subjects with missing values for this parameter will be considered non-responders.

8.2.1.2 Secondary Variables

All secondary variables will be determined at 24 weeks after the end of treatment/principal observation period and at 1, 2, 3, 4, and 5 years after the end of treatment/principal observation period.

- Loss of HBeAg (defined as absence of HBeAg)
- HBsAg seroconversion (defined as loss of HBsAg and presence of anti-HBs)
- Loss of HBsAg (defined as absence of HBsAg)
- Quantitative serum ALT
- Proportion of normal serum ALT (defined as ALT measure \leq ULN)
- Quantitative HBV-DNA
- Suppression of HBV-DNA $< 100,000$ copies/mL ($< 20,000$ IU/mL), $< 10,000$ copies/mL ($< 2,000$ IU/mL), undetectable, and change from baseline
- Combined endpoints: HBeAg seroconversion and HBV-DNA $< 100,000$ copies/mL ($< 20,000$ IU/mL)
- Combined endpoints: HBeAg seroconversion and HBV-DNA $< 10,000$ copies/mL ($< 2,000$ IU/mL)
- HBeAg seroconversion (defined as absence of HBeAg and presence of HBeAb)

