5.3.2 Safety

Safety assessments will include symptom directed physical examination, vital signs, growth, neuro-psychiatric questionnaire (PEG-IFN-treated subjects only, post-baseline), review of concomitant medications, reported AEs and specified safety laboratory assessments of hematology, clinical chemistry, thyroid function, and urinalysis. Additional safety assessments will be determined from tabulations of dose adjustments and premature withdrawals from treatment for safety or tolerability reasons.

All subjects need to have an ophthalmological examination (*consisting of fundoscopic examination with dilation, visual acuity assessment, visual field testing (confrontation test is recommended for younger children), and color visual testing*) by an ophthalmologist (*pediatric ophthalmologist is recommended*) within 6 months prior to baseline. *During the study*, subjects treated with PEG-IFN will receive *additional* ophthalmological examination as per the schedules in Table 2 and Table 4. Any subject who develops ocular symptoms should receive a prompt eye examination by an ophthalmologist and additional examinations as necessary.

For females of childbearing potential, a pregnancy test will be performed within 24 hours prior to baseline or switch baseline. This could be performed at the baseline visit, provided that the result is available prior to randomization and commencement of treatment. Pregnancy testing will also be performed at any time secondary amenorrhea of more than 1 week occurs. In addition, subjects treated with PEG-IFN will have pregnancy tests performed as per the schedules in Table 2 and Table 4.

Measurements of growth must be taken using the same instruments in the same individual. A stadiometer with mean of three readings should be used for height measurement. For Group A and C subjects, at Weeks 12, 24, and 36, and for switch subjects at switch baseline, switch week (SW)12, SW24, and SW36 the investigator or

designee will provide IXRS with the subject's height and weight so that the BSA and dose can be provided.

Height will be collected from consenting biological parents. This information may be entered directly onto the eCRF and the eCRF may be considered as the source document.

During the extended long-term follow-up period, only the following safety data will be collected:

- Persisting AEs initially reported prior to follow-up Week 24 (including neurological and psychiatric events)

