- New-onset SAEs (including neuro-psychiatric events) and non-serious AEs of special interest related to PEG-IFN
- Deaths
- Growth: weight and height
- Thyroid function

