4.4.2 Secondary Efficacy Endpoints

The secondary efficacy analyses will be performed in the ITT population. No hierarchical or sequential testing will be used for secondary efficacy endpoints.

Several secondary parameters will be assessed at the end of treatment/principal observation period, 24 weeks after the end of treatment/principal observation period in primary CSR; in addition, during the extended LTFU period, i.e. at 1, 2, 3, 4 and 5 years after the end of treatment/principal observation period in final CSR.

Secondary efficacy endpoints include two types of endpoints:

- Binary endpoints:
 - HBeAg seroconversion (except HBeAg seroconversion at the time point of 24 weeks at the end of treatment/principal observation period)
 - Loss of HBeAg
 - HBsAg seroconversion
 - Loss of HBsAg
 - Normal ALT (defined as $ALT \leq ULN$, where each ULN is given by each laboratory)
 - Suppression of HBV-DNA:
 - $<20,000$ IU/mL
 - $<2,000$ IU/mL
 - Undetectable (defined as <29 IU/mL as per TAQMAN-HBV QUANT polymerase chain reaction (PCR) assay)
 - Combined endpoints:
 - HBeAg seroconversion and HBV-DNA $<20,000$ IU/ml
 - HBeAg seroconversion and HBV-DNA $<2,000$ IU/mL
- Continuous endpoints:
 - Quantitative serum ALT value, and its change from baseline
 - Quantitative HBV-DNA value, and its change from baseline
 - Quantitative HBeAg value, and its change from baseline
 - Quantitative HBsAg value, and its change from baseline

For all binary endpoints, missing values would be considered as non-responders. For all continuous endpoints, no imputation approach will be implemented to missing values.

Descriptive statistics of the secondary efficacy binary endpoints will be summarized by treatment group. P-values of these binary endpoints will be presented using Fisher's exact test.

Continuous endpoints will be descriptively summarized over time by treatment group. Graphs of continuous secondary endpoints and their corresponding 95% confidence intervals over time will be displayed by treatment group.

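### ALT endpoints are set for Years 1 to 5, but no ALT is scheduled after follow-up Week 24, and the SAP's missing-value rule would score nearly all children as not normal

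*Protocol*

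**What the plan says.** Endpoints. Protocol 8.1.2 includes in its secondary list "loss of HBsAg, quantitative serum ALT, proportion of normal ALT, quantitative HBV-DNA", with annual timepoints out to Year 5. Protocol 8.2.1.2 is firmer: "All secondary variables will be determined at 24 weeks after the end of treatment/principal observation period and at 1, 2, 3, 4, and 5" years, and the items beneath include quantitative serum ALT and "Proportion of normal serum ALT". SAP 4.4.2 carries normal ALT as a binary endpoint and "Quantitative serum ALT value, and its change from baseline" as a continuous one, with Years 1 to 5 reported in the final CSR.

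Missing data. SAP 4.4.2: "For all binary endpoints, missing values would be considered as non-responders". Continuous endpoints are not imputed.

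Measurement. ALT, AST and total bilirubin appear only in the clinical chemistry panel (protocol Tables 5 and 6). The chemistry row ends at follow-up Week 24 in every schedule table.

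Long-term safety. Protocol 5.3.2: "During the extended long-term follow-up period, only the following safety data will be collected", followed by a list that includes "New-onset SAEs (including neuro-psychiatric events) and non-serious AEs of special interest related to PEG-IFN". Protocol 7.2.3 names as the first event of special interest "Cases of an elevated ALT or AST in combination with either an elevated bilirubin or clinical jaundice".

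**The concern.** Two secondary endpoints are specified at five timepoints where the schedule supplies no measurement. The gap would not show up plainly as missing data. For the binary endpoint, the SAP's rule turns an untested child into a non-responder, so the final report could show ALT normalization dropping away after Week 24 purely because testing stopped. The protocol's background section describes the inactive carrier state partly by ALT returning to normal, so this would bear directly on how durable the benefit appears.

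Any ALT values that did exist in those years would be few and selected: repeats prompted by an abnormality, or chemistry drawn because a Group B child was switching to PEG-IFN. The safety side has a related weakness. Protocol 8.2.5.3 plans to report the incidence of new related events of special interest at Years 1 to 5, but nothing scheduled would detect the laboratory part of the liver event.

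**Working it through.** **1. Is the gap real, or a misread table?** For each schedule table the cells in the chemistry row were matched to the column headers.

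| Table | Group | Columns | Last chemistry mark |
|---|---|---|---|
| Protocol Table 2 / SAP Table 1 | A and C | 22 | follow-up Week 24 |
| Protocol Table 3 / SAP Table 2 | B | 14 | follow-up Week 24 |
| Protocol Table 4 / SAP Table 3 | Switch | 21 | switch follow-up Week 24 |

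Cells and headers agree in number in all six, so the blanks at Years 1 to 5 are not a shifted row. In the protocol tables the HBeAg, HBV-DNA, HBsAg and thyroid rows continue to Year 5, so blood is already drawn at those visits. Withdrawal does not fill the gap: under protocol 4.6.2 a child leaving after follow-up Week 24 has the Year 5 assessments, which contain no chemistry.

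**2. Denominators.** The plan's figure is 145 randomized 2:1. It reproduces: 10% versus 32%, 2:1, two-sided 0.05 and 80% power give 48 + 96 = 144 with a continuity correction (126 without). Splitting 145: 145 × 2/3 ≈ 97 in Group A and 145 × 1/3 ≈ 48 in Group B.

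**3. Extent.** Five annual clinic visits (Year 1.5 is by telephone): 5 × 145 = 725 child-visits without scheduled ALT in the randomized groups, or 5 × 160 = 800 including Group C. Both ignore attrition and switching.

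**4. Rule applied with scheduled data only.** Normal ALT is 0/97 versus 0/48 at each timepoint, Fisher p = 1.0. Quantitative ALT and its change from baseline have n = 0.

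**5. Where Group B values could come from.** Chemistry is drawn at switch baseline, which coincides with the last pre-switch visit (protocol 5.3), and through switch follow-up Week 24. A child may switch up to one year after Week 48. The latest switcher has chemistry until 52 + 48 + 24 = 124 weeks after the principal observation period, which is past Year 2 (104 weeks) but short of Year 3 (156 weeks). Group B could therefore have values at Years 1 and 2; Group A has no such source. Protocol 8.2.4.1 counts as non-responders those who switch before follow-up Week 24. It is silent on later switchers, and SAP 4.2 leaves visit windows to DAP Module 2.

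**6. How few values would matter.** With k normal results in Group B and none in Group A, the two-sided Fisher p for these small k is the probability that all k fall in Group B, C(48,k)/C(145,k):
- k = 1: 48/145 = 0.331
- k = 2: (48 × 47)/(145 × 144) = 0.108
- k = 3: (48 × 47 × 46)/(145 × 144 × 143) = 0.035

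The counts are assumed for illustration. Three such values would give a nominal difference favoring the untreated arm, produced by the schedule alone.

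**7. Liver event.** Protocol 7.1.3 requires ALT or AST above 3 × baseline, together with bilirubin above 2 × ULN or clinical jaundice. After follow-up Week 24 no ALT, AST, bilirubin or physical examination is scheduled.

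**The case against.** The best defense is that SAP 4.4.2 says only that several secondary parameters are assessed at the listed times. Its list also contains quantitative HBeAg and HBsAg, whose rows likewise stop at Week 24, so it cannot mean every item at every visit. A sensible analyst would omit an ALT table with no data rather than print zeros. That has weight for the SAP alone. It does not rescue the protocol: 8.2.1.2 covers all its secondary variables, ALT is among them, and quantitative HBeAg and HBsAg are not.

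Three stronger inferences should be resisted.
- A reader might take the closed list in protocol 5.3.2 as confirming that ALT was deliberately dropped. That list concerns safety data. ALT is an efficacy assessment under 5.3.1.1, and HBeAg and HBV-DNA are also absent from the list yet drawn every year.
- A reader might infer that flares or reactivation go unseen for 4.5 years. HBV-DNA, HBeAg and HBsAg are measured annually, CHB medication is recorded, and related SAEs, persisting events and deaths are reported. Non-switch Group B does not collect new events of special interest in those years (protocol Table 3 footnote), so the detection point concerns only Groups A, C and Switch.
- A reader might expect banked serum to supply the missing ALT. Protocol 5.4.1 keeps those samples to repeat a scheduled test that failed; at Years 1 to 5 there is no original chemistry sample. Other use is limited to exploratory biomarkers in consenting children.

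It is also fair that these endpoints are secondary, their p-values exploratory (protocol 8.2.5), and no testing hierarchy depends on them.

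**Conclusion.** The endpoint list and the schedule contradict each other and should be reconciled before the final analysis. As written, quantitative ALT at Years 1 to 5 has no scheduled data, and the SAP rule would score essentially all Group A, Group C and non-switch Group B children as not normal.

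A reader might infer a certain 0% in every group. The documents do not support that: unscheduled repeats, and chemistry from Group B children at switch baseline or on the switch schedule, could contribute a few values. This makes the A versus B comparison less trustworthy, because the contributions are selected and unequal between arms. The 0/97 versus 0/48 result assumes full enrollment at 145, no unscheduled values, and literal application of SAP 4.4.2.

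For the liver event, the supportable conclusion is that a low reported incidence in Years 1 to 5 would be hard to interpret. The primary endpoint, the Week 24 analyses and the primary CSR are not affected.

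**What to change.** Choose one of two routes.
- Add ALT at Years 1, 2, 3, 4 and 5 in protocol Tables 2 to 4 and SAP Appendix 2 Tables 1 to 3, taken at the blood draw already made for HBV serology and thyroid tests. AST and bilirubin from the same tube are optional; they are not endpoints but would make the liver-event incidence interpretable. The cost is an amendment, a slightly higher blood volume in protocol 5.4 and some laboratory expense, with no new visit.
- Delete the Year 1 to 5 ALT endpoints from protocol 8.1.2 and 8.2.1.2, SAP 4.4.2 and the synopsis copies. The cost is a text change and the loss of long-term biochemical response.

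In either case, state in SAP 4.4.2 that the non-responder rule does not apply to ALT at a visit where ALT was not scheduled, and say whether ALT drawn after a Group B child switches counts toward Group B.
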